visual analog scale (VAS) to assess ART adherence in which participants mark a 100 mm line to indicate their percent adherence to their antiretroviral medications over the previous 4 weeks (Buscher et al., 2011; Walsh et al., 2002). Responses on this VAS have been associated with pill taking with MEMS (Buscher et al., 2011; Walsh et al., 2002), pill count (Walsh et al., 2002), and pharmacy records (Buscher et al., 2011). 7) Assess whether each participant refilled their ART prescription for each month, the pharmacy that filled each prescription, and the medication. 8) Pharmacy records will be obtained (with participant permission) to confirm self-reported data. 9) Participants will be asked how many primary HIV care visits they had in the past 3 months using procedures and definitions used in a prior multisite study (Purcell et al., 2007). Medical records will be obtained with permission to confirm self-reports. 10) The *Modified Economic Form 90 AIR/ED* will be created for this study based on the Economic Form 90 AIR/ED (Bray et al., 2007; Miller and Del Boca, 1994; Scheurich et al., 2005; Tonigan et al., 1997) to collect patient data on all health care utilization within the past 180 days. 10) A Modified SASCAP (Zarkin, Dunlap et al. 2004) will be used to estimate the costs associated with services in the study conditions. The SASCAP (www.rti.org/sascap) assesses activity-level resource use and cost data for intervention staff, consultants, and non-labor resources (e.g., building space) used in the provision of intervention services. The SASCAP method reliably estimates the costs of intervention activities and the cost per participant. Zarkin and Dunlap have applied this micro-costing approach (Zarkin et al., 2003, 2005, 2008, 2010; Dunlap et al., 2010). 11) A multiple-choice test evaluating the HIV Education Course.

b. Study duration and number of study visits required of research participants.

Participants in the incentive group will receive the incentive intervention for two years. For all participants, assessments will be conducted at intake to determine eligibility and characterize participants. Outcome assessments will be conducted at intake, every 3 months throughout the 2-year intervention evaluation and every 6 months of the 1-year follow-up period.

c. Blinding, including justification for blinding or not blinding the trial, if applicable.

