Specific Aim. Assess the effectiveness of the incentive intervention for decreased or undetectable viral loads in promoting retention in HIV medical care. We will assess whether the participant attended at least 2 medical visits per year (Mugavaro et al. 2012; Y/N each year based on self-report and medical records).

Specific Aim. Assess the effectiveness of an empirically-based incentive intervention in promoting undetectable levels of viral loads, maintenance of antiretroviral prescriptions, consistent adherence to antiretroviral therapy, and retention in HIV care after the incentive intervention is discontinued. We will assess measures described above but at the two 6-month assessments during the year after the intervention ends.

Moderator Analysis Measures

Specific Aim. Determine if drug (cocaine or opiate) dependence, alcohol dependence, depression, health literacy, and impulsivity assessed at intake moderate viral load suppression and response to the incentive intervention. A dichotomous value (Y/N) for cocaine, opiate and alcohol dependence will be used as assessed by the CIDI. The total score on the TOFHLA will be used to assess health literacy. The total score on the Beck Depression Inventory will be used to assess depression. Log transformed k for each participant on the delay discounting task will be used to assess impulsivity.

Mediator Analysis Measures

Specific Aim. Determine if antiretroviral medication adherence as assessed by qualitative HRMS blood tests of 15 antiretroviral medications mediates the effect of the incentive intervention on viral load suppression. We will assess mediating effects of medication adherence as assessed by qualitative blood testing on viral load using the method of Baron and Kenny (1986) as described below.

Economic Outcome Measures

Specific Aim. Assess the costs of HIV medical care for Usual Care and Incentive groups. We will assess the total cost per participant of both study interventions including cost of the incentive program (see below). We expect that Incentive group costs will be higher relative to the Usual Care due to the incentive program and because we expect that the Incentive participants will have greater treatment engagement.

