Specific Aim. Assess the cost-effectiveness of the empirically-based incentive intervention for undetectable viral loads. We will assess incremental cost-effectiveness ratio (ICER) by dividing the difference in costs of two interventions by the difference in effects of the two interventions during the 2-year intervention evaluation period on viral load suppression (see below). The ICER can be interpreted as dollars spent per unit of desired outcomes gained. The Incentive Intervention should yield a better ICER.

Specific Aim. Assess the cost-benefit of empirically-based incentive intervention for undetectable viral loads. We will perform a Cost-Benefit Analysis (CBA) to examine the monetized benefits relative to costs for the Usual Care Control and Incentive intervention conditions. The economic outcomes are health care utilization during the 2-year intervention evaluation period (see below). We expect that the Incentive Intervention will yield greater economic benefits relative to its costs than the Usual Care Control.

Measures assessed repeatedly over time will be analyzed with a longitudinal logistic regression model. Within-person correlated outcomes will be handled using generalized estimating equations (GEE; Zeger, Liang, & Albert, 1988). Measures assessed once will be analyzed using logistic regression. The magnitude of effects will be expressed using odds ratios with 95% CI. Intent-to-treat analyses will be adjusted for covariates used for stratification (Pocock et al., 2002). Two-sided tests with p-values <.05 will be considered significant.

- b. Statistical plan including sample size justification and interim data analysis.

STATISTICAL ANALYSES

Measures assessed repeatedly over time will be analyzed with a longitudinal logistic regression model. Within-person correlated outcomes will be handled using generalized estimating equations (GEE; Zeger, Liang, & Albert, 1988). Measures assessed once will be analyzed using logistic regression. The magnitude of effects will be expressed using odds ratios with 95% CI. Intent-to-treat analyses will be adjusted for covariates used for stratification (Pocock et al., 2002). Two-sided tests with p-values <.05 will be considered significant.

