Cost Analysis. We will derive cost estimates following an activity-based approach (Drummond et al., 2005; Gold et al., 1996; Zarkin, Dunlap et al., 2004; Zarkin et al. 2005 Zarkin, Dunlap, et al., 2008; Dunlap et al., 2010). The total cost per participant of each intervention (HIV health care costs and incentive/feedback program costs) will be the sum of the costs of (1) staff labor, (2) incentive payments; (3) medication; (4) building space, and (5) other supplies or materials. The labor costs of each activity are equal to the product of the amount of time spent by each person on the activity and their hourly wage. We will multiply the unit cost of other intervention resources with the quantity used per activity. The total intervention cost for each participant is the cost per activity multiplied by the number of activities received by the participant. The mean across patients in a given intervention condition yields the intervention's mean per participant cost.

[figure not shown]
Cost-Effectiveness (CEA). Our CEA methodology follows a standard economic approach (Drummond et al., 2005; Dunlap, Zarkin, et al., 2010; Siegel et al., 1996; Zarkin et al., 1996, 1997, 2008). The primary cost-effectiveness outcomes will be the percentage of participants with undetected viral loads at 24 months (end of intervention) and at 36 months (post-intervention). The incremental cost-effectiveness ratio (ICER) is calculated by dividing the difference in costs of two alternatives by the difference in their effects of the two alternatives. The estimated ICER can be interpreted as dollars spent per unit of desired outcomes gained (e.g., \$900 per percentage point increase in participants with undetected viral loads). To gauge the sampling uncertainty of the ICERs, we will calculate confidence intervals via nonparametric bootstrap methods (Indurkha et al., 2001; Briggs et al., 2006). We will estimate cost-effectiveness acceptability curves (CEACs) using nonparametric bootstrap methods (Dunlap et al., 2008, 2010; Fenwick et al., 2001, 2006). The CEACs incorporate the inherent variability of the cost and effectiveness estimates and show the probability that a treatment is cost-effective as a function of the policy maker's intrinsic valuation or willingness to pay for the clinical outcome.

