Cost-Benefit (CBA). We will examine the monetized health care benefits relative to costs for the two intervention conditions. Because previous studies have shown that health care costs can be much higher in individuals with higher viral loads (e.g., Chen et al., 2006; Gebo et al., 2010), primarily due to higher non-antiretroviral medications and hospitalizations, we will focus on assessing and monetizing the potential differences in health care utilization during the 2-year intervention period for the incentive condition group relative to the usual care group. Health care utilization will be collected using the modified Economic Form 90 AIR/ED. Unit costs used in monetizing these economic outcomes will be drawn from literature and public data.

Sensitivity Analysis. We will conduct sensitivity analyses to assess whether the economic results are affected by changes in model parameters, such as assumptions made in estimating costs. We will perform one-way sensitivity analyses and examine the effect of changing one of the model parameters holding all other parameters constant, as well as n -way sensitivity analyses in which n parameters of the model are varied jointly.

POWER ANALYSIS

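### The cost-benefit analysis stops counting health care use at month 24, so any saving or rebound in the post-incentive year is left out of net benefit; a 36-month version should be added

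*Combined protocol and SAP*

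**What the plan says.** Section 7 sets the window of the cost-benefit analysis twice. Under Economic Outcome Measures: "The economic outcomes are health care utilization during the 2-year intervention evaluation period". Under Economic Analyses, Cost-Benefit (CBA), the focus is on monetising "differences in health care utilization during the 2-year intervention period". The comparison is stated as "We will examine the monetized health care benefits relative to costs for the two intervention conditions".

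The cost side takes in the program. The cost aim reads "We will assess the total cost per participant of both study interventions including cost of the incentive program", and the Cost Analysis paragraph describes each intervention's total as "HIV health care costs and incentive/feedback program costs", with medication among the components. Section 4b gives the incentive intervention a length of two years.

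Follow-up goes on for a third year with visits at months 30 and 36 (section 4a, Assessments). The Modified Economic Form 90 AIR/ED, which the analysis uses for health care use, is designed "to collect patient data on all health care utilization within the past 180 days". It stands in a list of assessments that may be done at all time points, including the 6-month follow-ups.

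The Cost-Effectiveness (CEA) paragraph measures its outcomes "at 24 months (end of intervention) and at 36 months (post-intervention". Post-intervention effects are a secondary objective in section 2.

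**The concern.** All incentive spending falls in months 0 to 24, and the benefit set against it is cut off at the same point. If suppression partly lasts after incentives stop, some of the return on that spending comes in year 3 and is not counted. If health care use rises when incentives stop, that loss is not counted either.

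The sponsor's own premises make this relevant. The CBA paragraph rests on health care costs being higher at higher viral loads, so what happens to viral load after month 24 bears on net benefit. The background reports that earlier incentive effects were not maintained, and the plan treats persistence as an open question. The opening summary makes wider use depend on the intervention being economically sound. A net benefit that cannot register either persistence or rebound gives only part of that answer.

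**Working it through.** **1. Horizons side by side**
- Incentive program and its cost: months 0 to 24 (section 4b; cost aim and Cost Analysis in section 7).
- Health care use in the cost-benefit analysis: months 0 to 24 (both statements in section 7).
- Cost-effectiveness aim under Economic Outcome Measures: effect on suppression over the two intervention years.
- CEA paragraph under Economic Analyses: suppression at month 24 and at month 36.
- Economic sensitivity analysis: model parameters such as cost assumptions; the time horizon is not named.

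Year 3 is 12 of 36 planned follow-up months (33%), and none of it enters the cost-benefit analysis.

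**2. Could the listed form cover year 3?** Two look-backs of 180 days give 2 × 180 = 360 of about 365 days, without overlap. This assumes that the form is given at both visits and that both take place on schedule.

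**3. The one program cost total in the documents.** Section 9 gives maximum incentive earnings of $7,300. This reproduces: $10 × 730 days = $7,300. Weekly calls at $5 over 104 weeks add $520, so C = $7,300 + $520 = $7,820. This is the maximum incentive and call payment for one participant. It leaves out staff, space, supplies and medication, so it is not the whole program cost.

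**4. Effect of the third year.** Let S be the yearly saving in health care use during the program and f the year-3 saving as a fraction of S. The documents give neither; both are assumptions. Year-3 HIV care and medication costs are taken as equal between the arms for this illustration.

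- Benefit over 24 months: 2S. Benefit over 36 months: (2 + f)S.
- For f > 0, the omitted share of the benefit is f/(2 + f).
- For f < 0, the 24-month benefit overstates the 36-month benefit by the factor 2/(2 + f).
- Break-even yearly saving on C: $7,820/2 = $3,910 at 24 months and $7,820/(2 + f) at 36 months.

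| f | 24-month benefit against 36-month benefit | Break-even S at 36 months |
|---|---|---|
| -1 | overstated, 2/1 = 2 times | $7,820/1 = $7,820 |
| -0.5 | overstated, 2/1.5 = 1.33 times | $7,820/1.5 = $5,213 |
| 0 | same | $7,820/2 = $3,910 |
| 0.25 | 0.25/2.25 = 11% omitted | $7,820/2.25 = $3,476 |
| 0.5 | 0.5/2.5 = 20% omitted | $7,820/2.5 = $3,128 |
| 1 | 1/3 = 33% omitted | $7,820/3 = $2,607 |

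**5. Can the sign change?** Net benefit on these payments alone is 2S − C at 24 months and (2 + f)S − C at 36 months.
- S = $250 × 12 = $3,000: $6,000 − $7,820 = −$1,820 at 24 months. At 36 months it is $9,000 − $7,820 = +$1,180 if f = 1, and $7,500 − $7,820 = −$320 if f = 0.5.
- S = $400 × 12 = $4,800: $9,600 − $7,820 = +$1,780 at 24 months. At 36 months it is $7,200 − $7,820 = −$620 if f = −0.5, and $4,800 − $7,820 = −$3,020 if f = −1.

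So the sign can change in either direction under assumed values. The documents do not say which case applies.

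**The case against.** The strongest reply is that the window is a stated choice. Both places in section 7 agree, and program and benefit run over the same two years, so the analysis asks whether the program pays for itself while it runs. That is a legitimate question, and this part of the reply stands.

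A reader might infer more than the documents support in four ways.

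- **That the analysis is wrong.** It is not. A within-intervention horizon is permissible; it is unexplained and leaves out a year that the trial follows.
- **That observed data are being discarded.** The form is only permitted at months 30 and 36. Year-3 health care use is not yet a committed data set.
- **That the two economic analyses flatly conflict.** The cost-effectiveness aim also uses a two-year effect. Only the later CEA paragraph reaches month 36, and there it takes suppression at a time point, not costs or use accumulated over 36 months. The plainer mismatch is between the two cost-effectiveness statements.
- **That net benefit is understated.** The background on effects fading after incentives end makes f near zero or below at least as plausible as f = 1. At f = 0 year 3 adds nothing, though only year-3 data could show that.

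It is also true that this is one secondary economic analysis. The primary outcome and power are untouched, and post-intervention clinical outcomes are already analysed. What remains is that no planned result brings the post-incentive year into net benefit.

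**Conclusion.** The point holds as an incomplete horizon, not as an error. The cost-benefit analysis is limited to the two intervention years and cannot register a saving or a rebound in the third.

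The size and direction cannot be derived from the documents, which give no health care saving and no persistence fraction. Conditional on an assumed f, the 24-month figure is unaffected at f = 0, too low for f > 0 and too high for f < 0. The dollar break-evens apply only to maximum incentive and call payments for one participant. They illustrate sensitivity to the horizon and do not estimate what the program must save. This is a cheap improvement that could alter the economic conclusion; nothing in the primary analysis depends on it.

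**What to change.** - Keep the 24-month cost-benefit analysis and add a 36-month version, in both Economic Outcome Measures and the CBA paragraph.
- Commit in section 4a to giving the Modified Economic Form 90 AIR/ED at months 30 and 36.
- In the 36-month version, carry both year-3 health care use and year-3 HIV care and medication costs, in both arms. The Cost Analysis treats HIV care and medication as costs, and the plan expects greater treatment engagement in the Incentive group. Extending the benefit side alone could therefore bias the 36-month result.
- Count each item once: an HIV care visit reported on the form should not enter both the cost and the benefit side.
- Report both horizons when judging economic soundness.
- Reconcile the two-year effect in the cost-effectiveness aim with the month-24 and month-36 outcomes in the CEA paragraph.

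The cost is some wording and one added analysis. No new visit or instrument is needed, though the form becomes a commitment at two visits. The 36-month result will have more missing data and more variance, which is a reason to keep the 24-month result beside it.

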Mediation analysis. We will assess potential mediating effects of medication adherence as assessed by qualitative blood testing on viral load using the method of Baron and Kenny (1986). Specifically, this involves estimation of (1) the effect of treatment assignment (incentives) on undetectable viral load without controlling for medication adherence, (2) the direct effect of incentives on medication adherence, and if these two steps yield clinically and statistically significant effects, 3) the effect of incentives on viral load after controlling for medication adherence ($\text{logit } (Y_{ij}) = \beta_0 + \beta_1 x_i + \beta_{2-6} x_{2-6} + \beta_7 \text{adherence} + \epsilon_{ij}$). If medication adherence does mediate the effect of the incentives on presence of a detectable viral load, in this final model we would expect the effect of treatment (β_1) to be attenuated relative to the step 1 model, and for adherence (β_7) to be a clinically and statistically significant predictor of presence of a detectable viral load.

Missing data. We expect to collect $\geq 80\%$ of 3-month assessments (see below). Our primary approach will be to impute all missing values as the adverse outcome (e.g., detectable viral load). Model parameter estimates from this approach will be compared to a method without imputation. If these methods yield differing results, conclusions will need to be tentative. To investigate sensitivity to missing values, participants with and without missing values will be compared by covariates and treatment assignment.

ECONOMIC ANALYSES

We will use the provider perspective using a modified SASCAP and the research team's financial records. Intervention activities will be captured with the modified Economic Form 90 AIR/ED.

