The primary outcome measure of undetectable viral loads will be analyzed with a longitudinal logistic regression model using GEE (Diggle & Diggle, 2002). We used Liu and Liang (1997) to determine the total N required to detect a difference between groups with 80% power. The adjacent figure shows the total number of participants (N) required to detect a difference of 15% between the Usual Care Control and the Incentive Group at the eight 3-month assessments during the intervention evaluation period. The figure shows different percentages for the Usual Care Control group because that value affects the sample size required. 15% is smaller than the effects produced in all prior studies of voucher reinforcement of cocaine or opiate abstinence or medication adherence and smaller than all effects produced by the Therapeutic Workplace and smaller than the incentive effects in promoting drug abstinence, medication adherence and other health behaviors as shown in three different meta-analyses (Petry et al., 2012; Prendergast et al. 2006; Lussier et al., 2006). The horizontal red lines show the number of participants planned based on the number of participants enrolled and randomized to the two groups without (top dashed line) and after adjusting for the anticipated rates of missing data (20% missing, bottom solid red line). Based on this analysis, we need to enroll and randomize 200 participants (horizontal dashed line) to ensure that we have sufficient sample sizes after adjusting for the rates of missing data. After adjusting for missing data (20% missing), this would yield a sample size of 160 participants (200 participants x 0.80 collected samples = 160 participants). The adjusted sample size of 160 participants (solid red line) is a little more than the maximum number of participants that would be required.

c. Early stopping rules.

The protocol can be stopped based on recommendations of the Scientific Advisory Committee overseeing this study. We will ask the Scientific Advisory Committee to recommend that the trial be stopped if a review of the adverse events suggests to any of the investigators that the number of related and unexpected adverse events is unacceptably high. The Scientific Advisory Committee will be allowed to request statistical analyses to compare the groups on the rates of different adverse events or to have the adverse event data summarized in other ways that they deem appropriate.

Risks

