a. Medical risks, listing all procedures, their major and minor risks and expected frequency.

There is essentially no risk above those of normal daily living associated with the incentives, or with the data collection procedures used in these studies.

Blood samples will be collected from participants in the Incentive group. Those participants will provide a maximum of 1 blood sample per week. The samples will be tested for viral load and will involve collecting up to 10 cc of blood per sample. Participants in both groups will provide blood samples every 3 months for the primary and secondary outcome measures. Each of those samples (25 cc in total) will be tested for viral load (10 cc), for the presence of antiretroviral medications (5 cc), and for CD4 Counts (10 cc). Taking blood may cause some discomfort, bleeding or bruising where the needle enters the body, and in rare cases, it may result in fainting. There is a small risk of infection. When possible, we will use data available in each participant's medical records to get recent viral load and CD4 counts measures instead of collecting blood samples at each assessment time point.

b. Steps taken to minimize the risks.

To protect confidentiality, all research participants are identified by participant identification codes (Participant IDs) consisting of their initials and sequentially-assigned participant numbers on most forms and data files, and not by their names. Picture ID cards are maintained by staff in a locked container, and kept in a locked, secured area when not in use. All research data are stored in locked areas accessible only to research staff and are not left unattended. Documents with confidential information are shredded before being discarded. Confidential information is never given to anyone outside of the research program without the explicit written permission of the research participant. Only selected designated staff members are approved to give confidential information out after obtaining explicit written permission from the

participant. All research staff are trained in these procedures. We collect only general information about participant activities, legal and illegal. We do not collect information about specific illegal acts. To further protect confidentiality, we will obtain a confidentiality certificate from NIH to protect data collected in this study.

c. Plan for reporting unanticipated problems or study deviations.

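### The 80% power claim rests on 160 participants and a full 15-point difference, but the primary analysis keeps all 200 and codes missing samples as detectable

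*Combined protocol and SAP*

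**What the plan says.** Section 7b, Power Analysis, uses a GEE sample-size method "to determine the total N required to detect a difference between groups with 80% power", sized "to detect a difference of 15% between the Usual Care Control and the Incentive Group" over the eight 3-month assessments. It allows for 20% missing data by reducing the number of participants: "After adjusting for missing data (20% missing), this would yield a sample size of 160 participants", worked as "200 participants x 0.80 collected samples = 160 participants". It adds that 160 "is a little more than the maximum number of participants that would be required" across the control rates plotted, and it concludes from this that 200 must be randomized.

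Section 7b, Missing data, sets a different rule for the primary analysis: "Our primary approach will be to impute all missing values as the adverse outcome (e.g., detectable viral load". An analysis without imputation is planned only for comparison. Section 7 also specifies intent-to-treat and a significance rule: "Two-sided tests with p-values <.05 will be considered significant".

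**The concern.** Reducing N from 200 to 160 suits an analysis that discards missing observations: the difference stays the same and precision falls. Coding missing as detectable works differently. Nobody leaves the analysis, but with equal missingness each arm's undetectable rate, and hence the difference between arms, shrinks in proportion to the samples collected. If missingness differs by arm, that imbalance enters the treatment effect directly.

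The calculation in the plan therefore belongs to a different analysis from the primary one. It is the stated reason for enrolling 200. If the trial gives a null result, readers will rely on it to judge what the primary analysis could have detected.

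**Working it through.** **Inputs from the plan.** Two-sided 5% test, 80% power, 15 points, eight visits, 200 randomized, 20% missing, and a maximum required N slightly below 160.

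**Assumptions of this review.** 1:1 allocation, an exchangeable within-person correlation ρ, an unadjusted Wald test of the difference in proportions, and missingness unrelated to the outcome. The readable text gives neither ρ nor the control rates. They may be in the figure that is not available here, so their absence is not counted against the plan.

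**The plan's own figure.** 200 × 0.80 = 160, so the arithmetic is correct.

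**Solving for ρ.** With p1 = p0 + 0.15 and D = (1 + 7ρ)/8,

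N = 2(1.96 + 0.8416)²[p0(1−p0) + p1(1−p1)]D / 0.15².

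N is largest at p0 = 0.425, where the bracket is 2 × 0.425 × 0.575 = 0.48875 and N = 341.0 × D. Setting N = 160 gives D = 0.469 and ρ = 0.393.

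**Reading 1: 15 points is on collected samples, 20% missing in each arm.** The analysed difference is 0.8 × 0.575 − 0.8 × 0.425 = 0.12. Write m for the missing fraction, k = 1 − m and q = 1 − p. The variance V of a participant's mean over the eight visits, with missing coded as detectable, is:

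- whole participants lost: kpqD + kmp²
- visits missed independently: kp(1−kp)/8 + (7/8)k²ρpq
- progressive dropout: visit j observed with probability 1 − 2mj/9 (mean 1 − m), with covariances summed over visit pairs.

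Power = Φ(difference/√[(V0 + V1)/100] − 1.96). At p0 = 0.425 and m = 0.20:

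| Pattern | V0 + V1 | SE | Power |
|---|---|---|---|
| Independent visits | 0.1668 | 0.0408 | 0.836 |
| Progressive dropout | 0.2242 | 0.0474 | 0.717 |
| Whole participants | 0.2653 | 0.0515 | 0.644 |

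**Varying the assumptions** (power, same three patterns):

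| Setting | Independent | Progressive | Whole |
|---|---|---|---|
| p0 = 0.425, m = 0.10 | 0.860 | 0.801 | 0.766 |
| p0 = 0.425, m = 0.05 | 0.870 | 0.841 | 0.825 |
| p0 = 0.20, m = 0.20, ρ = 0.393 | 0.920 | 0.866 | 0.826 |
| p0 = 0.20, m = 0.20, ρ = 0.534 (N = 160 reached here) | 0.856 | 0.791 | 0.746 |
| p0 = 0.30, m = 0.20, ρ = 0.430 (N = 160 reached here) | 0.847 | 0.762 | 0.706 |

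At p0 = 0.425, power stays at 80% or more up to about 31% missing (independent), 10% (progressive) or 7% (whole participants).

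**Unequal missingness at p0 = 0.425.**

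- 15% missing in incentive and 25% in control: 0.85 × 0.575 − 0.75 × 0.425 = 0.170, power 0.92 to 0.99.
- The reverse: 0.75 × 0.575 − 0.85 × 0.425 = 0.070, power 0.27 to 0.40.

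**Reading 2: 15 points is already after imputation.** All 200 count. SE = √(0.48875 × 0.469/100) = 0.0479, and power = Φ(0.15/0.0479 − 1.96) = 0.879.

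**The case against.** The strongest reply is that the plan may be conservative. The text does not restrict the 15 points to collected samples. If it means the outcome as analysed, sizing on 160 leaves a margin and power is about 88%. The 160 also relates to an analysis the plan will run, since conclusions are to be tentative if the non-imputed results differ. Both points are fair, but neither makes the stated calculation match the primary analysis. The first shows that the reduction is not needed there. The second shows that the reduction belongs to the comparison analysis.

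Several objections to the size also stand:

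- ρ and the control rate are inferred or assumed, and the planned model is a covariate-adjusted logistic GEE, not a simple difference in proportions.
- Losing whole participants is the extreme pattern. The plan speaks of samples and assessments collected, and independently missed visits give 84%.
- 20% is a ceiling. At least 80% collection is expected, both arms are paid for follow-up assessments (Section 9), and medical records are to be used where possible "to get recent viral load and CD4 counts measures instead of collecting blood samples at each assessment time point" (Risks, Medical risks).
- The unequal-missingness cases are hypothetical.
- The plan regards 15 points as smaller than the prior effects it cites, so a larger true effect could make up the loss.

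Finally, the COVID-19 text in Section 4 refers to remaining assessments, so this version appears to date from late in the trial. Restating power would not change the estimate or the test. It would still change how a null or borderline result is read.

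**Conclusion.** The concern holds. The multiplication is right, but it is the wrong adjustment for the primary analysis on either reading of the 15 points. The effect on power is a range on both sides of 80%: about 64% to 84% on Reading 1 with equal 20% missingness at a 42.5% control rate, and about 88% on Reading 2. These figures depend on the inferred correlation, the assumed control rate and the pattern of missingness. Confidence is high in the mismatch and medium in its size. The documents do not establish a shortfall in power, only that the unqualified 80% is not supported for the analysis that will be reported as primary. It should be corrected.

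**What to change.** Rewrite the power paragraph for the primary analysis as planned: 200 analysed, with missing coded as detectable. State:

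- whether the 15 points is before or after imputation
- the within-person correlation and the range of control rates
- the assumed amount and pattern of missingness, separately by arm.

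Report the resulting range of power in place of the single 80% claim. If the 160 figure is kept, attach it explicitly to the comparison analysis without imputation.

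The primary missing-data rule should stay, and no added enrolment is needed. The cost is one recalculation and a few sentences in the protocol and SAP, and the stated power may look less favourable.
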